Tagraxofusp drug product is prepared as liquid or lyophilized formulations. The study site may be provided with either of the following:

- Tagraxofusp Injection is a preservative-free, sterile, clear, colorless solution supplied in single-dose glass vials containing 1 mL of sterile tagraxofusp solution (1 mg/vial) that should be stored in a freezer between -25°C and -15°C (-13°F and 5°F).
- Tagraxofusp for Injection (lyophilized powder), 1.0 mg is supplied in single-use, sterile, 2 mL glass vials packaged in labeled, single-vial cartons (study drug) and should be stored between 2°C and 8°C (36°F – 46°F).

Overall, tagraxofusp was generally well-tolerated in the clinical development program, and no evidence of cumulative toxicity with tagraxofusp has been seen. The most common treatment-emergent adverse events (TEAEs) with tagraxofusp include liver transaminase elevations; manifestations of capillary leak syndrome (CLS), including hypoalbuminemia, edema, and weight increases; hematologic abnormalities, primarily thrombocytopenia and anemia; nausea and other gastrointestinal symptoms; and constitutional symptoms.

Refer to the Investigator's Brochure for complete information on tagraxofusp.

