8.2.3.1 Capillary Leak Syndrome and Associated Symptoms

CLS is associated with vascular endothelial injury related to fusion protein administration and may occur 3 – 8 days after initiation of treatment.

Patients may exhibit symptoms of **hypotension**, fluid overload, evidenced by **weight gain** or edema, nausea, and anorexia, shortness of breath and, at times, confusion and muscle injury. Findings may include **hypoalbuminemia**, reductions in blood oxygen saturation, and evidence of pulmonary edema on chest x-ray. **These symptoms may present individually or as part of CLS.**

Refer to Appendix [Section 18.3](#) for management of patients with signs of CLS.

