11.10 Clinical Laboratory Tests

The following assessments should be done at the time points indicated in the applicable Schedules of Events ([Table 2](#) and [Table 3](#) for Stage 2; [Table 4](#) and [Table 5](#) for Stage 3A) and processed by the local laboratory.

- Hematology: Scheduled hematology assessments should at minimum include WBC count, differential WBC (lymphocytes, monocytes, basophils, eosinophils, and neutrophils), RBC count, hematocrit, Hb, platelet count and immature myeloid cells (including blasts + myelocytes + metamyelocytes + promyelocytes + nucleated red blood cells) (for safety assessments as well as for efficacy assessments at the end of each cycle in between bone marrow assessments).
- Serum albumin: May be a component of the serum chemistry panel. See Appendix [Section 18.3](#) for administration of albumin if serum albumin decreases to < 3.0 g/dL during treatment days or in the immediate post-treatment period.
- Serum chemistry and electrolytes: ALT, albumin, alkaline phosphatase (ALP), AST, bicarbonate, bilirubin (total, direct, and indirect), BUN, calcium, chloride, CPK, creatinine, glucose, LDH, magnesium, phosphate, potassium, sodium, total protein, and uric acid.
- Coagulation parameters: PT and/or INR and aPTT.
- Urinalysis (MF patients only): Appearance, color, pH, specific gravity, ketones, leukocytes, protein, glucose, bilirubin, urobilinogen, and occult blood.

Detailed instructions for collecting, processing, storing, and shipping the samples are provided in the Laboratory Manual.

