18.3 CLS Management Guidance

Time of Presentation	CLS Sign/Symptom	Recommended Action	Tagraxofusp Dosing Management
Prior to first dose of tagraxofusp in Cycle 1	Serum albumin < 3.2 g/dL	Administer tagraxofusp when serum albumin \geq 3.2 g/dL.	
	Serum albumin < 3.5 g/dL	Administer 25g intravenous albumin (q12h or more frequently as practical) until serum albumin is \geq 3.5 g/dL AND not more than 0.5 g/dL lower than the value measured prior to dosing initiation of the current cycle.	
During tagraxofusp dosing	Δ predose body weight that is increased by \geq 1.5 kg over the previous day's predose weight	
Administer 25g intravenous albumin (q12h or more frequently as practical), and manage fluid status as indicated clinically (e.g., generally with intravenous fluids and vasopressors if hypotensive and with diuretics if normotensive or hypertensive), until body weight increase has resolved (i.e. the increase is no longer \geq 1.5 kg greater than the previous day's predose weight).
 
Administer 25g intravenous albumin (q12h, or more frequently as practical) until serum albumin is \geq 3.5 g/dL.
	
Administer 25g intravenous albumin (q12h or more frequently as practical), and manage fluid status as indicated clinically (e.g., generally with intravenous fluids and vasopressors if hypotensive and with diuretics if normotensive or hypertensive), until body weight increase has resolved (i.e. the increase is no longer \geq 1.5 kg greater than the previous day's predose weight).
 
Administer 25g intravenous albumin (q12h, or more frequently as practical) until serum albumin is \geq 3.5 g/dL.

	Edema, fluid overload and/or hypotension	
Administer 1 mg/kg of methylprednisolone (or an equivalent) per day, until resolution of CLS sign/symptom or as indicated clinically.
 
Aggressive management of fluid status and hypotension if present, which could include intravenous fluids and/or diuretics or other blood pressure management, until resolution of CLS sign/symptom or as clinically indicated.
	
Administer 1 mg/kg of methylprednisolone (or an equivalent) per day, until resolution of CLS sign/symptom or as indicated clinically.
 
Aggressive management of fluid status and hypotension if present, which could include intravenous fluids and/or diuretics or other blood pressure management, until resolution of CLS sign/symptom or as clinically indicated.

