Analysis of AEs over time will be conducted by presentation of TEAE incidence by cycle. For this analysis, incidence per cycle will be based on the onset of a particular PT event within the cycle, where onset is indicated by first or repeat occurrence or increase in severity of the event within that cycle. This analysis will be conducted by maximum CTCAE Grade for each PT. AEs over time will also be presented by cycle for the incidence of TEAE leading to treatment discontinuation, dose reduction, and dose interruption by SOC and PT.

AEs of special interest (AESIs) will be determined using MedDRA version 19.0 standardized medical queries (SMQs), high-level terms, or PTs, as follows:

- Possible hypersensitivity events, based on the SMQ Hypersensitivity (broad search).
- Vascular capillary leak syndrome (CLS), in addition to PTs of hypoalbuminaemia, blood albumin decreased, and proteinuria.
- Visual acuity, based on the MedDRA PTs related to vision changes.
- Post-transplantation veno-occlusive disease, based on the MedDRA PTs pulmonary veno-occlusive disease and veno-occlusive liver disease.
- Possible drug-induced liver injury events, based on the SMQ drug-related hepatic disorders – comprehensive search (broad search).

Summary tables of AESIs will report AESI by PT, causality, severity grade, seriousness, and whether AESI led to discontinuation of study treatment. AESIs will also be included in data listings.

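### The SAP's capillary leak syndrome AESI term list does not match the protocol's own CLS signs, and a CLS event is left undefined in SAP 4.4.2.1

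*SAP*

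**What the plan says.** SAP 4.4.2 introduces its special-interest groups with "AEs of special interest (AESIs) will be determined using MedDRA version 19.0 standardized medical queries (SMQs), high-level terms, or PTs, as follows". The capillary leak entry reads "Vascular capillary leak syndrome (CLS), in addition to PTs of hypoalbuminaemia, blood albumin decreased, and proteinuria". The AESI tables are to be broken down by preferred term, causality, grade, seriousness and discontinuation. SAP 4.4.2.1 adds CLS-specific summaries: number and grade of events, time to first onset and to resolution, albumin infusions and their timing relative to onset, steroid use, recurrence, and CLS leading to discontinuation, reduction or interruption.

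The protocol describes the syndrome more widely. Protocol 4.4 refers to "manifestations of capillary leak syndrome (CLS), including hypoalbuminemia, edema, and weight increases". Protocol 8.2.3.1 says "Patients may exhibit symptoms of hypotension, fluid overload, evidenced by weight gain or edema, nausea, and anorexia", and adds hypoalbuminemia, reduced oxygen saturation and pulmonary edema as findings. It closes with "These symptoms may present individually or as part of CLS". The sign column of the table in Protocol 18.3 lists low albumin, "predose body weight that is increased by" at least 1.5 kg, and "Edema, fluid overload and/or hypotension".

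On urine testing, Protocol 11.10 has "Urinalysis (MF patients only" as a limit on that test, and neither Stage 3A schedule (Protocol Tables 4 and 5) has a urinalysis row.

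**The concern.** An AESI group exists to collect, under one label, the different ways in which a known toxicity may be recorded. Here the label is the protocol's, but the contents are not. The list keeps the laboratory sign, leaves out the fluid and hemodynamic signs, and adds a urine finding that the protocol does not associate with the syndrome. The SAP gives no reason.

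Safety is the first-listed objective of Stage 3A, and CLS is the only AESI with its own SAP subsection. If that subsection uses the whole list, isolated low albumin or proteinuria is counted, timed and followed to resolution as CLS. If it uses the syndrome term alone, everything rests on investigators choosing that term. Protocol 13.7 asks sites to report both symptoms and syndrome for hypersensitivity reactions; it makes no such request for CLS. The text does not tell the reader which of these two quantities will be reported.

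**Working it through.** The plan gives no figure to reproduce, and no rate, power or interval is involved. The check is a term-by-term comparison.

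| Item | Protocol 4.4 | Protocol 8.2.3.1 | Protocol 18.3, sign column | SAP 4.4.2 CLS list |
|---|---|---|---|---|
| Low albumin | yes | yes | yes | yes (two terms) |
| Edema | yes | yes | yes | no |
| Fluid overload | not named | yes | yes, same entry as edema | no |
| Weight increase | yes | yes | yes | no |
| Hypotension | not named | yes | yes, same entry as edema | no |
| Reduced oxygen saturation | not named | yes | not named | no |
| Pulmonary edema | not named | yes | not named | no |
| Proteinuria | not named | not named | not named | yes |

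**What the list does to individual patients.** Take the listed terms at face value.

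- CLS reported as such by the investigator: inside the group, through the syndrome term.
- Edema and hypotension reported, with no syndrome, albumin or proteinuria AE: outside.
- Hypoalbuminaemia alone: inside.
- Proteinuria alone: inside.

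The third case arises easily. Protocol 13.1.1 makes a laboratory result an AE when it requires medical intervention, and Protocol 18.3 links albumin below 3.5 g/dL during dosing to intravenous albumin.

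**Proteinuria.** Stage 3A has no scheduled urinalysis, whereas the Stage 2 schedules in Protocol Tables 2 and 3, presented for MF patients, do. SAP 3.5 displays safety by disease and stage, so the chance of finding this term is unequal between columns that will be read side by side.

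**Event definition in SAP 4.4.2.1.** There are two readings.

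- Syndrome term only. SAP 4.4.2 attaches the abbreviation CLS to the syndrome term and adds the other terms to it, so this reading is natural.
- Any term on the list. Low albumin could then both set the date of CLS onset and prompt the albumin infusion, which would make the planned summary of infusion timing relative to onset partly circular.

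The text does not choose between them. The search level for the syndrome entry (standardized query, high-level term or preferred term) is also unstated.

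**Where the omitted signs still appear.** SAP 4.4.2 tabulates all treatment-emergent AEs by system organ class and preferred term, and by cycle. SAP 4.4.4 flags systolic pressure below 90 mmHg with a fall of at least 20 mmHg; its table has no weight row. None of these tables shows two signs occurring together in one patient, although the by-patient listings would allow a manual check.

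**The case against.** The strongest case on the other side is that this is a matter of presentation. The AESI tables are by preferred term, so syndrome, albumin and proteinuria lines can be read separately, and no composite CLS rate is specified. Investigator-reported CLS is captured. The omitted signs are in the general AE tables. Protocol 8.2.3.1 itself separates a sign occurring alone from the syndrome, so adding every edema or hypotension term would count events that are not CLS. Protocol 18.3 is a management table, not a case definition. Protocol 13.1.1, which names the protocol's AESIs, does not include CLS, so the SAP contradicts no prespecified list. The analysis is descriptive.

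Much of this stands, and it rules out several stronger readings:

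- A reader might infer that the key toxicity is mis-measured. The documents do not show that: there is no CLS incidence, and 4.4.2.1 may already mean the syndrome term alone.
- A reader might call the group mainly an albumin endpoint. Low albumin readily becomes an AE, but nothing shows that it dominates, and reporting by term would expose it if it did.
- A reader might say that the SAP captures one of four signs in the management table. That count splits a single entry, edema with fluid overload and hypotension, into two and gives no credit for the syndrome term.
- A reader might infer a general difference between MF and CMML in urine testing. CMML patients enrolled under Amendment 6 or earlier follow a schedule that is not in these documents, so only the Stage 3A gap is established.

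What the objection does not answer is the inconsistency of the list. Specificity cannot explain leaving out edema and hypotension when isolated low albumin and proteinuria are let in. For hypersensitivity and liver injury, the same section uses deliberately broad searches.

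**Conclusion.** The mismatch holds. The list keeps low albumin, omits edema or fluid overload, weight increase and hypotension, and adds proteinuria, which the protocol's CLS text does not list and for which Stage 3A has no scheduled test. A CLS event in SAP 4.4.2.1 is undefined. The effect on the CLS rate cannot be sized and could go either way: sign clusters without the syndrome term are missed, while isolated laboratory findings may be counted.

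This rests on two assumptions: that the syndrome entry is not a wider query that already contains the omitted signs, which the SAP does not state, and that the separate output shells, which are not part of these documents, do not already settle the definition. As this is a descriptive safety summary with the signs visible elsewhere, the change is a worthwhile, cheap improvement and not the correction of a demonstrated error.

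**What to change.** 1. State the MedDRA search level for the syndrome entry. Define a CLS event in SAP 4.4.2.1 as the syndrome term (narrow group), and base count, grade, onset, resolution and recurrence on it.
2. Beside it, report a broad group labelled as possible CLS manifestations: the syndrome term, the two albumin terms, weight increased, edema and fluid-overload terms, hypotension, hypoxia and pulmonary edema. Mark it as supportive.
3. Preferably also show the number of patients with two or more of these signs in the same cycle, counting the two albumin terms as one sign. The protocol says that the signs can occur individually, so co-occurrence is the more informative quantity. The SAP already assigns AEs to cycles.
4. Take proteinuria out of the CLS group, or list it apart with a note on who had scheduled urinalysis.

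The cost is a revised term list, one definition and an extra AESI column, plus a small derivation for the same-cycle count; nothing new is collected. The broad group is less specific and will include events unrelated to capillary leak, so it should not replace the narrow one or be quoted as the CLS rate.

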4.4.2.1. Capillary Leak Syndrome

In addition to the summaries described in [Section 4.4.2](#), summaries will be provided that include:

- Summary of number of CLS events, number of CLS events by CTCAE Grade, and time to first onset and time to resolution of CLS events;
- Summary incidence of albumin infusions and timing of infusions in relation to CLS onset;
- Summary incidence of steroids used
- Summary incidence of recurring CLS
- Summaries of CLS leading to treatment discontinuation, dose reduction, and dose interruption

4.4.3. Laboratory Data

Clinical laboratory values will be expressed in Système International (SI) units and tabulations will be based on Safety Population.

The actual value and change from baseline (Day 1) to each on-study evaluation through cycle 6 will be summarized for each clinical laboratory parameter, including hematology, clinical chemistry, coagulation, and urinalysis. In the event of repeat values, the last non-missing value closest to the planned study day/time will be used. Box plots will also be presented.

Shift tables of change in CTCAE grade of laboratory parameters from baseline to worst value and from baseline to last value on study will be presented for each disease. Both scheduled and unscheduled visits will be included in shift tables.

To assess for possible drug-induced liver injury (DILI) (FDA 2009), alanine aminotransferase, aspartate aminotransferase, and total bilirubin results will be listed for patients that meet Hy's law criteria. Hy's Law case candidates are defined as subjects with peak ALT or AST $>3 \times$ upper limit of normal (ULN) and total bilirubin $>2 \times$ ULN within ± 7 days.

All laboratory data will be provided in by-patient data listings.

By-patient listings will also be presented for all laboratory values with CTCAE Grade ≥ 3 and for all clinically significant laboratory values with CTCAE Grade ≥ 3 .

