8.2 Study Treatment Administration Schedule

Patients will receive 12 mcg/kg of tagraxofusp by IV infusion once daily for 3 consecutive days (or 3 doses over a period not to exceed 10 days if postponement is required to allow for toxicity resolution) of a cycle in the absence of PD or other withdrawal criteria.

A treatment cycle is 21 days in C1-4 and 28 days in C5 and beyond.

The total per-patient dose is calculated based on patient body weight in kg at baseline (C1D1). This dose will be recalculated if there is a 10% or greater change from baseline in body weight.

The first cycle of tagraxofusp must be administered in the inpatient setting, with hospitalization beginning the day of the first infusion of tagraxofusp (or a prior day) and ending approximately 24 hours after the last infusion of tagraxofusp. Subsequent cycles of tagraxofusp can be administered in the inpatient setting or in a suitable outpatient ambulatory care setting that is equipped for intensive monitoring of patients with hematopoietic malignancies undergoing treatment, per the Investigator's discretion, institutional guidelines, and capabilities. Patients will be monitored for at least 1 hour (or longer at the Investigator's discretion) following the administration of each infusion of tagraxofusp in Cycle 2 and beyond.

Patients with evidence of ongoing disease control during treatment (without evidence of clinically significant PD or intolerable toxicity) may receive repeated cycles of tagraxofusp even if an overall response, in the judgment of the Investigator, is not attained.

Refer to [Section 8.2.1](#) for details regarding required pre-medication, patient monitoring procedures, and dose modification procedures for the management of tagraxofusp-related toxicity.

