8.2.2 Patient Monitoring Procedures During the Tagraxofusp Dosing Period

During each cycle, testing and procedures that may result in withholding of a scheduled tagraxofusp infusion, (largely based on unresolved manifestations of fluid retention and/or other relevant acute toxicities during daily dosing), include findings from clinical examination including but not limited to vital signs, and clinical laboratory parameters, detailed below, and as indicated in the applicable Schedules of Events ([Table 2](#) and [Table 3](#) for Stage 2; [Table 4](#) and [Table 5](#) for Stage 3A).

Vital Signs: Blood pressure, heart rate, respiration rate, body temperature, and pulse oximetry are to be measured during screening and during the dosing period (usually Days 1, 2, and 3) immediately prior to infusion, immediately after completion of infusion, and 30 and 60 minutes post-infusion; and at subsequent time points in each cycle as indicated in the applicable Schedules of Events ([Table 2](#) and [Table 3](#) for Stage 2; [Table 4](#) and [Table 5](#) for Stage 3A).

Diagnostic Tests:

- During the dosing period prior to tagraxofusp infusion (usually Days 1, 2, 3) and at subsequent time points in each cycle as indicated in the applicable Schedules of Events ([Table 2](#) and [Table 3](#) for Stage 2; [Table 4](#) and [Table 5](#) for Stage 3A): CBC with differential, platelets, sodium, potassium, chloride, bicarbonate, blood urea nitrogen (BUN), creatinine, glucose, total protein, albumin, calcium, phosphorus, uric acid, total bilirubin, ALT, AST, alkaline phosphatase, lactate dehydrogenase (LDH), prothrombin time (PT) or International Normalized Ratio (INR), aPTT (activated partial thromboplastin time). Additional evaluation of albumin or ALT/AST during days subsequent to treatment days may be indicated in situations where abnormalities (albumin decrease, ALT/AST increase) are noted subsequent to treatment.
- Serum albumin must be ≥ 3.2 g/dL prior to first dose of tagraxofusp in Cycle 1. During tagraxofusp dosing, serum albumin must be ≥ 3.5 g/dL. If serum albumin is reduced by ≥ 0.5 g/dL from the albumin value measured prior to tagraxofusp dosing initiation for the current cycle, withhold tagraxofusp infusion and administer 25g IV albumin. Interrupt tagraxofusp dosing until serum albumin is ≥ 3.5 g/dL AND not more than 0.5 g/dL lower than the value measured prior to dosing initiation for the current cycle.

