Table 7-3 Stage 3A: Study Events Schedule for Screening and Cycles 1-4 for Patients with CMML

Procedures	Day -28 to 0	Days 1-3 (Up to Day 10 if Infusion(s) Held) Tagraxofusp Treatment		Cycle 1 Day 8±3 ¹	Day 21±3 ²	Day 28±3, Then Every 7±3 days (Only if Delayed End of Cycle: for Toxicity Resolution)
		Screening	Pre-Infusion	Tagraxofusp Infusion		
Informed consent form ³	X					
Inclusion/exclusion criteria ³	X					
Medical history	X					
12-lead ECG	X					
ECOG performance status	X	X (Infusion 1, C1)			X	X
Physical examination, including assessment for hepatomegaly and splenomegaly	X			X	X	
Pregnancy test ⁴	X					
Vital signs and weight ⁵	X	X	X	X	X	X
MUGA scan or 2-D Echocardiogram ⁶	X					
Hematology ⁷	X	X		X	X	X
Serum chemistry ⁸	X	X		X	X	X
Coagulation parameters: PT/INR, aPTT ⁹	X	X		X	X	X
Peripheral blood for flow cytometry	X	X (Infusion 1)		X		
Peripheral blood for IL-10 testing		X (Infusion 1, C1)			X C1 and C4	
Peripheral blood for translational studies (select centers)		X (Infusion 1, C1)			X C1 and C4	
Bone marrow aspiration/biopsy ¹⁰	X				X C1 and C4 ¹¹	
MRI or CT for assessment of hepatomegaly and splenomegaly ¹²	X				X C1 and C4 ¹¹	
Immunogenicity sampling ¹³		X (Infusion 1)			X	

Procedures	Day -28 to 0	Days 1-3 (Up to Day 10 if Infusion(s) Held) Tagraxofusp Treatment		Cycle 1 Day 8±3 ¹	Day 21±3 ²	Day 28±3, Then Every 7±3 days (Only if Delayed End of Cycle: for Toxicity Resolution)
		Screening	Pre-Infusion			
Cytogenetic and molecular genetic testing	X				X C1 and C4	
Administration of premedications ¹⁴		X				
Tagraxofusp administration ¹⁵				X		
MPN-SAF TSS evaluation ¹⁶	X				X	
Baseline/tumor response assessment ¹⁷	X				X C1 and C4 ¹¹	
Vision assessment	X				X	
Prior/concomitant medications/therapies (including concomitant platelet and RBC transfusions)	X	X	X	X	X	X
AE and SAE monitoring	X	X	X	X	X	X

AE = adverse event; aPTT = activated partial thromboplastin time; CT = computed tomography; ECG = electrocardiogram; ECOG = Eastern Cooperative Oncology Group; INR = international normalized ratio; MPN-SAF TSS = Myeloproliferative Neoplasm Symptom Assessment Form Total Symptom Score; MUGA = multigated acquisition; PT = prothrombin time; SAE = serious adverse event.

- 1 Day 8 visit is required for C1 only and must be performed at the site.

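### The Hy's Law screen is anchored on the peak ALT or AST and its terms are undefined, so a later same-day rise in enzyme and bilirubin can go unlisted

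*SAP*

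**What the plan says.** SAP 4.4.3 plans a listing of ALT, AST and total bilirubin for patients who meet Hy's Law criteria. Hy's "Law case candidates are defined as subjects with peak ALT or AST" above 3 × ULN, with bilirubin above 2 × "ULN within ± 7 days". It does not say whether the peak is taken over the whole study, a cycle or an episode, or which date anchors the window. It does not say whether unscheduled samples count, although the same section states that they do for the shift tables.

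The sampling schedule matters here. Under Protocol 8.2.2, chemistry is drawn "During the dosing period prior to tagraxofusp infusion (usually Days 1, 2, 3) and at subsequent time points in each cycle as indicated" in the schedules of events. Protocol 8.2 adds that "A treatment cycle is 21 days in C1-4 and 28 days in C5 and beyond". SAP Tables 7-3 and 7-4 place an end-of-cycle chemistry draw at Day 21 or Day 28, plus one at Cycle 1 Day 8 ("Day 8 visit is required for C1 only and must be performed at the site"), one at end of treatment, and further draws in delayed cycles: "Day 28±3, Then Every 7±3 days (Only if Delayed End of Cycle: for Toxicity Resolution". ALT, AST and bilirubin belong to one panel.

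Protocol 4.4 states: "The most common treatment-emergent adverse events (TEAEs) with tagraxofusp include liver transaminase elevations".

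**The concern.** Treatment is repeated over many cycles and raises transaminases often. Protocol 8.2.3.3 withholds dosing above 5 × ULN only for the rest of that cycle, so exposure can resume and a patient may have more than one enzyme elevation. A rule tied to the highest value looks for bilirubin around one date and ignores the other elevations, even those where both thresholds are crossed in one sample.

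What is at stake is the completeness of one safety listing. Drug-induced liver injury is an adverse event of special interest in SAP 4.4.2, and this listing is the only planned output that joins the enzyme result to the bilirubin result. The undefined terms also mean that two programmers could produce different lists from the same data.

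**Working it through.** The plan gives no figure for this screen, so there is none to reproduce. The check has three parts.

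**1. Gaps between scheduled chemistry draws**, from the visit days and ±3-day windows in SAP Tables 7-3 and 7-4, with no cycle delay:

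| From | To | Nominal gap | With visit window |
|---|---|---|---|
| C1 Day 3 | C1 Day 8 | 8 − 3 = 5 days | 2 to 8 |
| C1 Day 8 | C1 Day 21 | 21 − 8 = 13 days | 7 to 19 |
| C2–4 Day 3 | Day 21 | 21 − 3 = 18 days | 15 to 21 |
| C5 on, Day 3 | Day 28 | 28 − 3 = 25 days | 22 to 28 |

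If dosing runs to Day 10, the last gap in the cycle is 8 to 14 days (to Day 21) or 15 to 21 days (to Day 28). So from Cycle 2, with no delay, no scheduled bilirubin falls in the 7 days after the last dosing-period draw. An end-of-cycle peak is different: it has bilirubin in the same sample, and the next cycle's draws follow 1 to 3 days later.

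**2. The rule applied to three constructed patients.** These are illustrations, not trial data. Values are multiples of ULN, and ALT and AST are taken to move together. Cycle 2 starts on study day 22 and Cycle 3 on day 43.

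- A: day 8 (C1 Day 8) ALT 8, bilirubin 0.8; day 45 (C3 Day 3) ALT 4, bilirubin 2.5.
- B: day 24 (C2 Day 3) ALT 6, bilirubin 0.9; day 42 (C2 Day 21) ALT 1.5, bilirubin 2.6; day 43 (C3 Day 1) ALT 1.3, bilirubin 2.2.
- C: as B for day 24; day 42 ALT 3.5, bilirubin 2.6; day 43 ALT 3.2, bilirubin 2.2.

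| Rule | A | B | C |
|---|---|---|---|
| One peak per subject, ±7 days (literal) | no | no | no |
| One peak per subject, ±21 days | no | yes | yes |
| Any value above 3, ±7 days | yes | no | yes |
| Any value above 3, ±30 days | yes | yes | yes |

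A fails the literal rule because the bilirubin rise is 45 − 8 = 37 days from the peak, although both thresholds are crossed in one sample. Widening the window to 21 days does not help A; dropping the peak does. B is a matter of the window alone (42 − 24 = 18 days). A per-cycle reading would list A, and would list C only through the Cycle 3 Day 1 sample (3.2 with 2.2), so the two readings give different lists.

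Extra testing can also work against the patient. Protocol 8.2.2 says "Additional evaluation of albumin or ALT/AST during days subsequent to treatment days may be indicated in situations where abnormalities" are seen; bilirubin is not among the tests named. In Cycles 2–4 at nominal timing, the Day 3 bilirubin reaches forward to Day 10 and the Day 21 bilirubin back to Day 14. An ALT-only peak on Days 11 to 13 therefore has no scheduled bilirubin in its window, and under the literal rule it displaces a Day 21 sample in which both tests are raised.

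**3. How often the peak could sit in the wrong cycle.** Suppose ALT or AST exceeds 3 × ULN in m cycles and bilirubin rises in one of them. If the peak is equally likely to be in any of the m cycles, the chance that it is in another one is 1 − 1/m: 50% for m = 2, 67% for m = 3, 75% for m = 4. If bilirubin always rises with the highest enzyme value, the chance is 0%. The documents do not say where between these ends the truth lies.

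**The case against.** The strongest reply is that little is lost. Every scheduled ALT and AST has a same-day bilirubin, so a rise concurrent with the peak is caught. SAP 4.4.3 also plans by-patient listings of all laboratory data and of Grade 3 or higher values, and worst-value shift tables that include unscheduled visits. The liver-injury search in SAP 4.4.2 is a broad SMQ search that does not use this definition, and Protocol 13.1.1 makes laboratory abnormalities reportable when they lead to further testing or treatment. All of this stands and limits the consequence. It does not close the gap: the shift tables are by individual parameter, the full listing classifies nobody, and the SMQ search depends on an event having been reported.

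A reader might go further and infer that real liver-injury cases are being missed, or that the study report will wrongly state there were none. The documents contain no patient results of this kind and plan a listing, not such a statement. Nor is it right that every bilirubin rise first seen at an end-of-cycle draw after Cycle 1 escapes: if the enzyme peak is in that sample or in the next cycle's first draws, the two pair. The miss needs an earlier peak outside the window.

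The long gap after dosing is also partly a sampling limit of the protocol, which no analysis rule can fully repair.

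**Conclusion.** The definition is ambiguous and, on its literal reading, can leave out patients who cross both stated thresholds in the same sample. That is a defect in the anchor, and it holds whatever the window. It rests on reading the peak as one per subject, which the text allows and does not exclude.

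The mismatch between 7 days and the 18- and 25-day nominal gaps is a secondary point. It affects only patients whose enzyme is raised in the dosing period and whose bilirubin rises later, after the enzyme has fallen back.

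The number of patients affected cannot be estimated. The 50% to 75% figures assume exchangeable cycles and repeated elevations, fall to 0% if bilirubin tracks the peak, and should not be quoted as rates for this trial. The change is worth making because it is cheap and the listing has no substitute.

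**What to change.** Redefine a candidate in SAP 4.4.3 as a patient with any post-dose ALT or AST above 3 × ULN and total bilirubin above 2 × ULN within 7 days before or after the date of that ALT or AST value, using scheduled and unscheduled samples. Keeping at least 7 days in both directions means that no patient flagged on a post-dose peak drops out; a forward-only window would lose bilirubin rises that come shortly before the enzyme rise.

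Optionally, add a sensitivity listing with a longer forward window, showing the gap in days and the ALP result. Twenty-eight days would cover the longest undelayed gap in the schedule. A window that long can pair values from different cycles, so it suits a supplementary listing for medical review better than the main definition.

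The cost is one SAP sentence, one listing program and a few more candidates to review by hand. No new data are needed.
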